#### Table 7. **Other Effectiveness Analyses**

Endpoint	Description	Analysis Period	Methodology
ATHS responder status as assessed by EI	Number (%) of responders	CP, TP	Binomial descriptive statistics
Raw value and change from baseline in ATHS score as assessed by EI (based on the worse temple, or the left temple if both temples have the same baseline score)	Summary	CP, TP	Continuous descriptive statistics
GAIS responder status as assessed by EI	Number (%) of responders	CP, TP	Binomial descriptive statistics
Responses on GAIS as assessed by EI	Number (%) by response category	CP, TP	Frequency counts and percentages
GAIS responder status as assessed by participant	Number (%) of responders	CP, TP	Binomial descriptive statistics
Responses on GAIS as assessed by participant	Number (%) by response category	CP, TP	Frequency counts and percentages
Raw value and change from baseline in FACE-Q Satisfaction with Facial Appearance Rasch-transformed score as assessed by participant	Summary	CP, TP	Continuous descriptive statistics
Responder status in FACE-Q Satisfaction with Facial Appearance Rasch-transformed score as assessed by participant	Number (%) of responders (improved)	CP, TP	Binomial descriptive statistics
Responses on item A, F, J of FACE-Q Satisfaction with Facial Appearance	Number (%) by response category (including somewhat satisfied or very satisfied)	CP, TP	Binomial descriptive statistics
Responses on each item of FACE-Q Satisfaction with Facial Appearance	Number (%) by response category	CP, TP	Frequency counts and percentages

#### Table 7.Other Effectiveness Analyses (Continued)

Endpoint	Description	Analysis Period	Methodology
Raw value and change from baseline in FACE-Q Satisfaction with Temples Rasch-transformed score as assessed by participant	Summary	CP, TP	Continuous descriptive statistics
Responder status in FACE-Q Satisfaction with Temples Rasch-transformed score as assessed by participant	Number (%) of responders (improved)	CP, TP	Binomial descriptive statistics
Responses on item 2, 4, 11, 12 of FACE-Q Satisfaction with Temples	Number (%) by response category (including somewhat satisfied or very satisfied)	CP, TP	Binomial descriptive statistics
Responses on each item of FACE-Q Satisfaction with Temples	Number (%) by response category	CP, TP	Frequency counts and percentages
Participant responses to satisfaction with treatment on a 5-point scale	Number (%) by response category for treatment group only (including satisfied or very satisfied)	TP	Frequency counts and percentages
Participant responses to natural look of the treatment areas on a 5-point scale	Number (%) by response category for treatment group only (including satisfied or very satisfied)	TP	Frequency counts and percentages
Participant responses to natural feel of the treatment areas on a 5-point scale	Number (%) by response category for treatment group only (including satisfied or very satisfied)	TP	Frequency counts and percentages
Participant responses to treatment meeting expectation (yes/no)	Number (%) by response category for treatment group only	TP	Binomial descriptive statistics
Participant responses to interest to continue to use the treatment (yes/no)	Number (%) by response category for treatment group only	TP	Binomial descriptive statistics
Participant's willingness to recommend treatment (yes/no)	Number (%) by response category for treatment group only	ТР	Binomial descriptive statistics
Volume change of each temple (left temple, right temple) from baseline as assessed by 3D imaging	Summary	CP, TP	Continuous descriptive statistics

#### Table 7. Other Effectiveness Analyses (Continued)

Endpoint	Description	Analysis Period	Methodology
Participant's self-perception of age	Change from baseline for treatment group; for control group at baseline only	CP, TP	Continuous descriptive statistics; with paired t-test within treatment group at Month 6

## 8.6 Effectiveness Subgroup Analyses

Not applicable.

# 9.0 Safety Analyses

#### 9.1 General Considerations

- For CP, safety summaries will be performed on the safety population. Subjects will be included in the analysis according to the study treatment that they actually received.
- For TP, safety summaries will be performed on the VIT and VOT populations. Subjects will be included in the analysis according to the study treatment that they actually received.
- The baseline for safety parameters will be the last non-missing assessment prior to or on Day 1, i.e., the latter of randomization or initial injection in Control Period. Day 1 is defined as the day on which the study intervention (VOLUMA or no-treatment control) is first received.
- Study day refers to Day 1 regardless of study period (e.g., CP, TP).
- The change from baseline values will be computed as the postbaseline value minus the baseline values.
- Adverse events (AEs) will be coded using the Medical dictionary for Regulatory Activities (MedDRA). The actual version of the MedDRA coding dictionary will be noted in the statistical tables and clinical study report.

#### 9.2 Adverse Events

#### 9.2.1 Treatment-Emergent Adverse Events

An AE will be considered a treatment-emergent adverse event (TEAE) if the AE began or worsened (increased in severity or became serious) on or after the first administration of study intervention (i.e., on or after study Day 1 defined in Section 7.1).

A treatment-emergent serious adverse event (TESAE) is defined as a serious adverse event (SAE) that is also a TEAE.

#### 9.2.2 Adverse Event Overview

TEAEs will be summarized by treatment group for CP using the safety population. TEAEs will also be summarized by treatment group for TP using the VIT and VOT populations, respectively as described in Table 8. The summaries will be presented using number and percentage of participants with TEAEs as well as the number of events. Additional summaries may be provided when applicable.

An overall summary of TEAEs will be presented as described in Table 8.

A TEAE will be considered a treatment-related TEAE if the TEAE is deemed as related to the study procedure or the study device by the TI. Treatment-related AEs will be summarized by duration, severity, time to onset on/after the most recent treatment, and outcome.

The duration of an AE is defined as the end date of AE minus the start date of AE plus 1.

If more than 1 AE is coded to the same preferred term for a participant, the participant will be counted only once for that preferred term using the most severe and most related occurrence for the severity and relationship to study intervention summaries, respectively.

If the severity of a TEAE is missing, the maximum severity will be assigned to the event for the summary on severity. The value will be displayed as missing in the data listing.

If the relationship to the study intervention is missing for a TEAE, the event will be considered related to the study intervention for the summary. The value will be displayed as missing in the data listing.

Listings of all AEs, TESAEs, TEAEs leading to discontinuation, and death will be presented.

Endpoint	Description	Timing	Methodology
Overall summary	
 
Overall summary only for the following categories:
 
TEAEs
 
Treatment-related TEAEs
 
Treatment-related TEAEs at injection site
 
Treatment-related TEAEs not at injection site
 
TESAEs
 
Treatment-related TESAEs at injection site
 
Treatment-related TESAEs at injection site
 
Treatment-related TESAEs not at injection site
 
Treatment-related TESAEs not at injection site
 
TESAEs at injection site
 
Treatment-related TESAEs not at injection site
 
Treatment-related TESAEs not at injection site
 
TesAEs leading to study discontinuation
 
Deaths
 
	CP, TP	Frequency counts and percentages
TEAEs	

By SOC and PT

By SOC, PT, and maximum severity

	CP, TP	Frequency counts and percentages
Treatment -related TEAEs	
 
By SOC and PT
 
By SOC, PT and maximum severity
 
By duration, time to onset from the most recent treatment, action taken and outcome and categorized by severity
 
	CP, TP	Frequency counts and percentages
TESAEs	By SOC and PT	CP, TP	Frequency counts and percentages
AEs leading to study discon- tinuation	By SOC and PT	CP, TP	Frequency counts and percentages

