#### Table 1-1 Screening Visit Procedures: All Participants

Procedure	Screening within 30 days
Consent	Х
Participant demographics	Х
Height, weight, and vital signs a	Х
Medical/surgical/cosmetic/dental history	Х
Lab testing (urinalysis, hematology, chemistry)	Х
Pregnancy test b	Х
ATHS (EI) c	Х
Inclusion/exclusion criteria	Х
Adverse events	X
Concomitant medications, procedures, therapies	X

Note: All screening procedures must be performed onsite.

a Includes blood pressure (systolic and diastolic; while participant is seated), respiratory rate, pulse rate, and temperature.

c TI will use EI ATHS scores to confirm participant's eligibility in the study.

<sup>b For female participants of childbearing potential; administered and confirmed negative prior to randomization or study intervention. A female is not considered of childbearing potential if she has been postmenopausal for at least 1 year or does not have a uterus at the time of study entry. Can be urine or blood pregnancy test according to site requirements.

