# CONFIDENTIAL JUVÉDERM® VOLUMA® with Lidocaine injectable gel

Note: If the participant is not able to present in-clinic to the site due to national or regional travel restrictions, site closure as a result of these restrictions, or a participant declines an in-clinic visit due to pandemic or natural disaster-related health concerns, a telephone or virtual visit is permitted. However, if a participant is later able to present in-clinic to the site within the visit window, assessments may be performed in-clinic and the data will be captured for the visit.

- a All follow-up visits are scheduled from the date of the last treatment: If no touch-up treatment is performed, initial treatment will also be the last treatment.
- b All study exit procedures are to be performed for participants who withdraw from the study.
- c All screening procedures (including pregnancy test) must be performed before randomization; randomization must occur before initial treatment.
- d For female participants of childbearing potential; administered and confirmed negative before randomization or study intervention. Pregnancy testing need not be repeated if study pregnancy testing has been conducted within 7 days before randomization/initial treatment. In post-control period to be conducted only at study exit visit. A female participant is not considered of childbearing potential if she has been postmenopausal for at least 1 year or does not have a uterus at the time of study entry. Can be urine or blood pregnancy test according to site requirements.
- e The TI may perform a touch-up treatment if agreed upon by both the participant and TI. Touch-up treatment is recommended if the TI thinks that optimal correction has not been achieved.
- f Must be completed before randomization.
- g Must be completed before study interventions.
- h Performed at Month 6 visit only.
- i If participants exit the study before Month 6, then lab testing is needed at Exit Visit.
- j The 30-day daily safety diaries are to be completed following each treatment starting on the day of treatment and are considered complete if all days are completed until the visit 1 month after treatment.
- k Assessment on Day 14 after each treatment will be recorded along with safety diaries, while for other visits it will be performed on-site.

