# CONFIDENTIAL JUVÉDERM® VOLUMA® with Lidocaine injectable gel

- Note: If the participant is not able to present in-clinic to the site due to national or regional travel restrictions, site closure as a result of these restrictions, or a participant declines an in-clinic visit due to pandemic or natural disaster-related health concerns, a telephone or virtual visit is permitted. However, if a participant is later able to present in-clinic to the site within the visit window, assessments may be performed in-clinic and the data will be captured for the visit.
- a During the control period all follow-up visits are scheduled from the date of randomization.
- b During the post-control period, all follow-up visits are scheduled from the date of the optional last treatment: If no touch-up treatment is performed, optional initial treatment will also be the optional last treatment.
- c All screening procedures (including pregnancy test) must be performed before randomization; randomization must occur before initial treatment.
- d For female participants of childbearing potential; administered and confirmed negative before randomization or study intervention. Pregnancy testing need not be repeated if study pregnancy testing has been conducted within 7 days before randomization. Pregnancy testing to be conducted only at treatment visits and study exit visit. A female participant is not considered of childbearing potential if she has been postmenopausal for at least 1 year or does not have a uterus at the time of study entry. Can be urine or blood pregnancy test according to site requirements.
- e Must be completed before randomization.
- f Must be completed before study interventions.
- g The TI may perform a touch-up treatment if agreed upon by both the participant and TI. Touch-up treatment is recommended if the TI thinks that optimal correction has not been achieved.
- h Performed at Month 6 after last treatment only. If participants exit the study after last treatment in the postcontrol period, then laboratory testing is needed at Exit Visit.
-  The 30-day daily safety diaries are to be completed following each treatment starting on the day of treatment and are considered complete if all days are completed until the visit 1 month after treatment.

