# 8.2.1. Clinical Safety Laboratory Assessments

Hematology and blood chemistry tests will be performed as described in Appendix 10.2.

At screening, the TI will assess the clinical significance of any values outside the reference ranges provided by the laboratory, and participants with abnormalities judged to be clinically significant will be excluded from the study.

The TI must review the laboratory report and document this review and record any clinically relevant changes occurring during the study in the AE section of the eCRF. The laboratory reports must be filed with the source documents. Clinically significant abnormal laboratory findings are those that are not associated with the underlying disease, unless judged by the TI to be more severe than expected for the participant's condition.

All laboratory tests with values considered clinically significantly abnormal during participation in the study are to be repeated until the values return to normal or baseline or are no longer considered clinically significant by the investigator.

- If such values do not return to normal/baseline within a period of time judged reasonable by the investigator, the etiology is to be identified and the sponsor notified.
- All protocol-required laboratory assessments, as defined in Appendix 10.2, must be conducted in accordance with the SoA (Section 1.3).
- If laboratory values from non-protocol specified laboratory assessments performed at the institution's local laboratory require a change in participant management or are considered clinically significant by the investigator (eg, SAE or AE or dose modification), then the results must be recorded as an SAE or AE in the eCRF.
- Urine or blood pregnancy tests will be used at the study site at screening, before each study treatment, and at study exit for female participants of childbearing potential.
- If a participant who underwent at least 1 treatment withdraws from the study before the Month 6 visit, he/she must be followed up for hematology test, clinical chemistry, and routine urinalysis at study exit for safety.

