# Table 2.Definition of the Control and Treatment Periods by Analysis Group
(as-randomized for effectiveness or as-treated for safety)

Analysis Group	Period	Analysis Group Label	Start Date	End Date
VOLUMA	СР	VOLUMA	Initial treatment date	
 
The end date is the date of the Month 6 assessment:
 
If multiple assessments fall into Month 6 window, the date of the assessment included in the Month 6 analysis will be used as end date.
 
For participants who exit before Month 6, the end date is study exit date.
 
For participants with a missing assessment at Month 6, the end date is the target day for Month 6 (180 days from preceding treatment).
 

	TP	VOLUMA	Initial treatment date	Study exit date
Control	СР	Control	Randomization date	
 
For participants who do not receive optional treatment:
 
If multiple assessments fall into Month 6 window, the date of the assessment included in the Month 6 analysis will be used as end date.
 
For participants who exit before Month 6, the end date is study exit date.
 
For participants with a missing assessment at Month 6, the end date is the target day for Month 6 (180 days from preceding treatment).
 
For participants who receive optional treatment, the end date is the date when the treatment is received.
 

	ТР	VOLUMA Post-Control	Optional initial treatment date	Study exit date

For CP, effectiveness analyses and baseline characteristics will be performed on the mITT population using the "as-randomized" assignment.

For TP, effectiveness and safety summaries will be performed on the VIT and VOT population for each treatment group.

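### The by-arm control-period TEAE table can contain adverse events found by scheduled laboratory testing in the VOLUMA column only, because controls have no scheduled follow-up laboratory tests in that period

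*SAP*

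**What the plan says.** **Who is tested, and when.** Both arms have urinalysis, hematology and chemistry at screening (Protocol Table 1-1). In Table 1-2 (treatment group) the laboratory row is next marked in the Month 1/3/6 column, under the control period, with footnote h: "Performed at Month 6 visit only". Footnote i covers early leavers: "If participants exit the study before Month 6, then lab testing is needed at Exit Visit". In Table 1-3 (control group) the only mark in the laboratory row is in the last, post-control column, with footnote h: "Performed at Month 6 after last treatment only". Protocol 8.2.1 ties the exit sample to having been treated; its condition reads "If a participant who underwent at least 1 treatment withdraws from the study before the Month 6 visit".

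**What happens to a finding.** Under Protocol 8.2.1 the treating investigator must review the laboratory report and "record any clinically relevant changes occurring during the study in the AE section of the eCRF".

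**When the control period ends.** For the VOLUMA group, SAP 5.1 Table 2 says: "The end date is the date of the Month 6 assessment"; for those who leave earlier it is the study exit date. For controls it is the Month 6 assessment date, the exit date, or the date of optional treatment.

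**How events are tabulated.** SAP 9.2.2 says: "TEAEs will be summarized by treatment group for CP using the safety population". Table 8 gives this overall and by SOC and PT. No rule flags or separates events found through laboratory testing. Laboratory values are listed, not summarized (SAP 9.3).

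**The concern.** The control-period TEAE table is the main tabulated safety comparison of VOLUMA with concurrent untreated controls. The treatment-period tables use the VIT and VOT populations, both of which have been injected. A reader will take a difference between the two control-period columns as information about the device.

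For events that a blood or urine sample would reveal, the columns are not ascertained alike: the schedule looks once in one arm and never in the other. With identical true rates of laboratory abnormality, the VOLUMA column could still show more. Because SAP 9.2.2 counts an event with missing relationship as related, such events could also enter the treatment-related rows. With laboratory values only listed, no planned summary would tell the reader that the difference came from testing one arm.

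**Working it through.** The plan states no figure to reproduce. The check traces the schedule and then illustrates the size.

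**Step 1. Scheduled safety laboratory tests between screening and the end of the control period**

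| | VOLUMA | Control |
|---|---|---|
| Month 6 of the control period | 1 (Table 1-2, footnote h) | 0 (Table 1-3) |
| Exit before Month 6 | 1 in place of Month 6 (Table 1-2, footnote i; 8.2.1) | 0 (8.2.1 requires at least one treatment) |
| Total per participant | 1 | 0 |

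Pregnancy tests in controls are not safety laboratory panels. Unscheduled tests are allowed in either arm (Protocol Appendix 10.2) and do not change the scheduled count.

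**Step 2. Do such events fall in the control period?** For VOLUMA completers the sample belongs to the Month 6 visit, and the control period ends on the date of the Month 6 assessment. It is therefore normally taken on the period's last day. Early-exit samples sit on the same kind of boundary. The SAP does not say whether the end date is inclusive, or whether a laboratory event is dated to the sample, the report or the investigator's review. An event dated later appears only in the treatment-period table. For controls, every possible end of the control period comes before their first scheduled follow-up sample.

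**Step 3. Size.** Inputs: 112 VOLUMA and 56 control participants randomized; 90 VOLUMA participants expected to be evaluable at Month 6 (Protocol 9.2). The rate q of clinically relevant new abnormality at the sample is not in the documents, so 1%, 3% and 5% are assumed.

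- Expected VOLUMA participants with such an event: n × q.
- Probability of at least one: 1 − (1 − q)^n.
- Share of the VOLUMA column: n × q / 112.

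| q | n = 90: expected | P(at least one) | points of 112 | n = 112: expected | P(at least one) | points of 112 |
|---|---|---|---|---|---|---|
| 1% | 90 × 0.01 = 0.9 | 60% | 0.8 | 1.1 | 68% | 1.0 |
| 3% | 90 × 0.03 = 2.7 | 94% | 2.4 | 3.4 | 97% | 3.0 |
| 5% | 90 × 0.05 = 4.5 | 99% | 4.0 | 5.6 | 99.7% | 5.0 |

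The counts and points assume that every such event is dated within the control period. The points are before any overlap with other TEAEs in the same participant. At the same rates, 56 controls would carry 56 × q = 0.6, 1.7 or 2.8 such abnormalities, none of which scheduled testing could detect in the control period.

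**The case against.** The strongest case against acting has five parts.

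- **Not every abnormality becomes an event.** The investigator must judge the change clinically relevant, and screening excludes participants with clinically significant abnormalities that would affect the study. This stands. A reader might infer that the table will show a VOLUMA excess by construction. The documents support only that it can, and only if the event is dated inside the control period.
- **Not all 112 will be tested.** Month 6 planning assumes 90, early discontinuation visits take place only if possible (Protocol 7.2), and missed blood draws have no remote substitute (Protocol 8.2). This stands, so 112 is an upper bound.
- **Much is already visible.** TEAEs are tabulated by SOC and PT, all AEs and laboratory values are listed, and no between-arm test or success criterion rests on the table. This lowers the stakes. But a PT row does not show how an event was found, nor that one arm had no scheduled test.
- **Removing these events from the main table would be worse.** It would lower the treated arm's headline count and depart from Protocol 9.4.5.1, whose summary covers all TEAEs. This stands, and it is why the full table should remain.
- **No re-sorting creates a control sample.** This also stands. A reader might hope that separating the events would reveal whether VOLUMA affects laboratory values. It would not. Nor would the columns become alike in every respect, since injection reactions cannot occur in untreated controls; the plan already splits injection-site events.

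The SAP itself accepts the general principle. Its version history (13.0) explains that SAP 9.9 reports TEAEs with and without one site because that site recorded all ISRs as AEs. That reporting difference lies between sites, while randomization is within site. The laboratory difference lies between arms and has no equivalent handling.

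**Conclusion.** The point holds as a matter of unequal ascertainment in a descriptive safety table. Scheduled control-period follow-up laboratory tests are one per VOLUMA participant and none per control, and the plan carries clinically relevant findings into a by-arm TEAE table without marking them.

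The likely size is modest: about 1 to 6 VOLUMA participants, or 0.8 to 5 percentage points of that column, at assumed rates of 1% to 5% with 90 to 112 tested. This rests on three assumptions: the rate, which the documents do not give; the number actually tested; and dating of the event on or before the control-period end date. The documents do not show that any such event will occur, and they give no reason to doubt the effectiveness analyses.

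**What to change.** In SAP 9.2.2 and Table 8:

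1. Keep the full control-period TEAE table as planned, with a footnote that controls had no scheduled follow-up laboratory testing in the control period.
2. Flag AEs identified from the protocol-scheduled Month 6 or exit laboratory sample.
3. State that flagged AEs are dated to the sample and that the control-period end date is inclusive. For controls injected on that same date, SAP Table 2 starts the treatment period on the same day, so also state to which period same-day events belong.
4. Add a supportive by-arm control-period TEAE summary, overall and by SOC and PT, without the flagged AEs.
5. Show the flagged AEs in a VOLUMA-only table.

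The cost is SAP wording, one flag and two extra tables. The documents describe no AE-source field, so the flag would have to be derived, for example from the sample date and the investigator's laboratory review. No visit or sample is added, and no event leaves the main table. What remains unsolved is that a real laboratory effect still cannot be compared between arms.
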